Cumulative incidence of pancreatic insufficiency after the onset of CP are presented by Kaplan-Meier survival curves. Log-rank test is further used to analyze the difference of cumulative rates of pancreatic insufficiency between two groups. *P* values for pairwise comparisons were adjusted using the Bonferroni correction. Cox proportional hazards regression model is used to identify the potential risk factors. Hazard ratios and 95% confidence intervals are calculated. All statistical tests are 2-sided. Data are analyzed using SPSS 23.0 (SPSS Inc, Chicago, IL) and SAS 9.4 (SAS Institute, Cary, NC).

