Over the past two decades, it has been increasingly appreciated that genetic factors also played an important role in the development of CP. The rare pathogenic variants in susceptibility genes of CP, such as *SPINK1* (encoding pancreatic secretory trypsin inhibitor), *PRSS1* (encoding cationic trypsinogen), *CTRC* (encoding chymotrypsin C) and *CFTR* (encoding cystic fibrosis transmembrane conductance regulator) genes, are overrepresented in both ICP and ACP, and related to earlier onset of CP.⁸⁻¹² However, few studies focused on the effect of genetic factors on the progression of CP. A prospective study conducted by Muller et al found that patients carrying *SPINK1* mutations had longer delay from onset of disease to pancreatic endocrine and exocrine insufficiency development. Another study by Frulloni et al also concluded exocrine and endocrine insufficiency occurred less frequently and later in CP patients with genetic mutations (*CFTR* and *SPINK1*) than those without. Onversely, Sun et al concluded that

CP patients carrying *SPINK1* c.194+2T>C mutation developed diabetes mellitus (DM) significantly since onset of CP.¹⁵ These discrepancies may be attributable to the small numbers of enrolled patients, the different racial backgrounds, and the analysis of limited genes and pathogenic variants. As far as we knew, there are no published studies investigating the influences of both environmental and genetic factors on the progression of CP.

2 Objectives

The study aims to investigate the comprehensive impact of both environmental and genetic factors on the progression of CP, defined as the development of either endocrine or exocrine insufficiency following the onset of CP.

3 Study setting

The study is designed as a prospective observational study and conducted in Changhai Hospital, which is a tertiary referral center and the largest CP medical center in China.

4 Eligibility criteria

Inclusion criteria

Consecutive patients with a diagnosis of CP and agreed to provide a blood sample for genetic tests are enrolled between January 2010 and December 2014.

Exclusion criteria

- 1) autoimmune pancreatitis;
- 2) pancreatic cancer diagnosed within two years following the onset of CP;
- 3) patient had less than two years' follow-up;
- 4) patients presenting with diabetes and/or steatorrhea at onset of CP.

5 Study design

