If inclusion/exclusion criteria are met and written informed consent has been obtained, the patient will be enrolled in the present study and the following data are documented in detail: demographic data (date of birth, gender), alcohol consumption and smoking history, family history, age at disease onset, etiologies of CP, CP-related complications, laboratory and imaging results, and treatment.

All enrolled patients agreed to provide a blood sample for genetic tests. All known rare pathogenic variants of the *PRSS1*, *CFTR*, *SPINK1*, and *CTRC* genes are included in the final analysis. The detailed DNA preparation methods, gene sequencing, and pathogenic variants inclusion criteria have been described previously. Patients with at least one rare pathogenic variant are considered genetic factor/s

positive (denoted as G+).

Patients are considered smokers if they had smoked ≥ 100 cigarettes before the onset of CP. Additionally, based on their alcohol consumption patterns before the onset of CP, the patients are categorized into four groups, abstainers, light drinkers (≤ 20 g/d), moderate drinkers (≥ 20 g/d), and heavy drinkers (≥ 80 g/d). Patients with a history of either smoking or alcohol consumption are considered environmental factor/s positive (denoted as E+).

During follow-up, aside from visits owing to complaints of discomfort caused by CP, all patients will be periodically (annually at least) contacted for clinical and imaging (computed tomography or magnetic resonance imaging) check-ups. The examination results, any changes in alcohol consumption or smoking status, and CP complications are also recorded. Data for the present study will be obtained in 2020. The follow-up time is defined as the duration from the onset of CP (first clinical symptoms attributable to CP or first imaging procedure showing CP lesions) to the end of follow-up, last personal contact, diagnosis of pancreatic cancer, regional or total pancreatectomy, or death, whichever came first. All patients are prospectively observed from enrolment until the cessation of follow-up.

6 Outcomes

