The primary endpoint is the development of pancreatic insufficiency (diabetes and/or steatorrhea). The components of the primary endpoint (diabetes and steatorrhea) are set as the secondary endpoints. Patients with diabetes and/or steatorrhea during the course of CP are considered to have pancreatic insufficiency. Diabetes is diagnosed according to the criteria of the American Diabetes Association, as follows: (1) hemoglobin A1C ≥6.5% (48 mmol/mol); or (2) fasting plasma glucose ≥126 mg/dL (7.0 mmol/L). Fasting is defined as no caloric intake for at least 8h; or (3) 2-h plasma glucose ≥200 mg/dL (11.1 mmol/L) during oral glucose tolerance test (OGTT), which is performed using a glucose load containing the equivalent of 75-g anhydrous glucose dissolved in water; or (4) in a patient with classic symptoms of hyperglycemia or hyperglycemic crisis, a random plasma glucose ≥200 mg/dL (11.1 mmol/L). Steatorrhea is diagnosed according to one of the following conditions: (1) chronic diarrhea with foul-smelling, oily bowel movements or (2) a positive result in a standard quantification test (fecal fat excretion of greater than 14 g/d). ¹⁶

7 Data management

Data collection

Clinical data regarding demographic data (date of birth, gender), alcohol consumption and smoking

history, family history, age at disease onset, etiologies of CP, CP-related complications, laboratory and imaging results, and treatment are collected during the first hospital admission

Statistical analysis

For continuous variables, tests of data normality are carried out using the Shapiro-Wilk test. Normally-distributed variables are presented as mean \pm standard deviation (SD) and compared using Student's t-test. And non-normally distributed data are presented as median (interquartile range, IQR) and compared using Mann-Whitney U test. Categorical variables results are presented as frequency and percentage. Chi-squared analysis or Fisher's exact test is used for comparison.

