Cumulative incidence of pancreatic insufficiency after the onset of CP are presented by Kaplan-Meier survival curves. Log-rank test is further used to analyze the difference of cumulative rates of pancreatic insufficiency between two groups. *P* values for pairwise comparisons were adjusted using the Bonferroni correction. Cox proportional hazards regression model is used to identify the potential risk factors. Hazard ratios and 95% confidence intervals are calculated. All statistical tests are 2-sided. Data are analyzed using SPSS 23.0 (SPSS Inc, Chicago, IL) and SAS 9.4 (SAS Institute, Cary, NC).

8 Ethics approval

Ethical approval is obtained from Changhai Institutional Review Board with the ID of CHEC2020-142.

9 Funding

Support for this study come from the National Natural Science Foundation of China (Grant Nos. 81970560[[name]], 82070661 [[name]], 81873588[[name]]), Scientific Innovation Program of Shanghai Municipal Education Committee (No. 201901070007E00052[[name]]), and Clinical Research Plan of SHDC (SHDC2020CR2032B).

10 Declaration of interests

The authors declare that they have no competing interests.

11 References

- Singh VK, Yadav D, Garg PK. Diagnosis and Management of Chronic Pancreatitis: A Review.
 Jama 2019;322:2422-2434.

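### Kaplan-Meier curves are labelled cumulative incidence although cancer, pancreatectomy and death end follow-up, so they overstate insufficiency before those events wherever such events occur

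*Combined protocol and SAP*

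**What the plan says.** The SAP, and protocol section 7 (Statistical analysis) in the same words, state: "Cumulative incidence of pancreatic insufficiency after the onset of CP are presented by Kaplan-Meier survival curves". On the group comparison both add: "Log-rank test is further used to analyze the difference of cumulative rates of pancreatic insufficiency between two groups". Cox regression is then used to look for risk factors.

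Time runs from onset of chronic pancreatitis. Under protocol section 5 it stops at the end of follow-up, the last personal contact, or "diagnosis of pancreatic cancer, regional or total pancreatectomy, or death, whichever came first".

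The primary endpoint in section 6 is diabetes and/or steatorrhea, and each component is a secondary endpoint. Cancer, pancreatectomy and death are not part of it. Section 6 also says: "Patients with diabetes and/or steatorrhea during the course of CP are considered to have pancreatic insufficiency".

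Three further statements bear on the size of the problem. Patients "are enrolled between January 2010 and December 2014". Section 4 excludes "pancreatic cancer diagnosed within two years following the onset of CP" and anyone with under two years of follow-up. Section 5 says: "Data for the present study will be obtained in 2020".

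Neither the protocol nor the SAP mentions competing events, names an estimator that allows for them, or plans to count them by group.

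**The concern.** Readers will take a curve labelled cumulative incidence as the share of patients who have developed insufficiency by a given time from onset. Kaplan-Meier with cancer, pancreatectomy and death censored does not estimate that share. It treats patients removed by those events as if they still faced the same risk of insufficiency as those who remain.

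The plan also leaves its target open. Three readings are possible:

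- insufficiency before any of these events;
- insufficiency at any time in the course of the disease, which the section 6 wording suggests;
- a natural course in which surgery does not happen.

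These can give different numbers. Kaplan-Meier targets the third only if the terminating events are independent of insufficiency risk, which the plan does not state.

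At stake are the absolute rates read from the curves, the absolute gaps between genetic and environmental groups, and the description of what the tests compare.

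**Working it through.** The plan gives no incidence, event count or competing-event rate, so it has no figure to reproduce. All hazards below are assumptions. The endpoint, terminating events, time origin, exclusions and dates come from protocol sections 4 to 6.

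**Direction.** One minus Kaplan-Meier (1-KM) accumulates the insufficiency hazard weighted by survival free of insufficiency alone. The cumulative incidence function (CIF) weights it by survival free of insufficiency and of every terminating event. The second weight is never larger, so 1-KM is never below the CIF. It is strictly above once an insufficiency event follows a terminating event among patients at risk.

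**When competing events can occur.** Read literally, the two exclusions leave no competing event in the first two years from onset. A patient enrolled in 2010-2014 also cannot have died before enrolment, so long-standing cases carry extra death-free time. I therefore start competing events at s = 2 and at s = 5 years (enrolment five years after onset). Cancer or surgery before enrolment is not ruled out by the dates, so the later start applies mainly to death.

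**Formulas.** With insufficiency hazard a and competing hazard b:

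- 1-KM(t) = 1 − exp(−at)
- CIF(t) = 1 − exp(−as) + exp(−as) × a/(a+b) × [1 − exp(−(a+b)(t−s))]

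**Example.** Take a = 0.05, b = 0.04, s = 2, t = 10. CIF = 0.0952 + 0.9048 × 0.5556 × 0.5132 = 0.353, and 1-KM = 1 − exp(−0.5) = 0.393. The gap is 4.0 points.

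**Overstatement at 10 years, a = 0.05 per year (1-KM = 39.3%)**

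| Competing hazard per year | Start year 2 (points) | Start year 5 (points) |
|---|---|---|
| 0.0025 | 0.3 | 0.1 |
| 0.005 | 0.5 | 0.2 |
| 0.01 | 1.1 | 0.4 |
| 0.02 | 2.1 | 0.8 |
| 0.04 | 4.0 | 1.5 |

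At 5 years the gap is 0.0 to 0.7 points (start year 2). With a from 0.03 to 0.08 and b from 0.005 to 0.04, the 10-year gap is 0.4 to 5.2 points (start year 2) or 0.1 to 1.9 (start year 5). For a single component at 0.02 to 0.04 per year it is 0.3 to 3.5 or 0.1 to 1.3.

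**Simulation with the plan's dates.** Enrolment was uniform over 2010-2014 with a data cut in mid-2020. Onset-to-enrolment time was exponential with an assumed mean of 2, 5 or 8 years, and n was 400,000 per setting. The 10-year gap was 0.9, 0.6 or 0.5 points at b = 0.01, and 3.5, 2.3 or 1.7 points at b = 0.04.

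**Separate check.** With 1-KM fixed at 40% at 10 years and a net terminating-event risk of 10% from year 2, a simulation of 200,000 patients gave 1-KM 40.1%, Aalen-Johansen 38.7% and an observed proportion of 38.7%.

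**Group differences at 10 years.** With an assumed hazard ratio of 1.5 (0.05 against 0.075), Kaplan-Meier shows exp(−0.5) − exp(−0.75) = 13.4 points. The CIF differences are:

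| Competing hazard, reference / exposed | Start year 2 (points) | Start year 5 (points) |
|---|---|---|
| 0.005 / 0.02 | 11.3 | 12.6 |
| 0.02 / 0.005 | 14.8 | 14.0 |
| Equal, 0.005 to 0.02 | 12.9 to 13.3 | 13.2 to 13.4 |

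**Insufficiency at any time.** Assume pancreatectomy at 0.02 and death at 0.005 per year from year 2. If the insufficiency hazard after surgery is multiplied by 0.5, 1, 2 or 5, the 10-year probability is 37.8%, 38.8%, 40.4% or 43.3%, against 39.3% by Kaplan-Meier. The sign is open. Before any competing event it is 36.7%.

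I give no figure beyond 10 years. Reaching year 20 by 2020 needs onset by 2000, hence about nine or more death-free years before enrolment.

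**The case against.** The strongest reply is that the overstatement refers to a quantity the plan never names. The plan speaks of insufficiency after onset and during the disease course, and on the any-time reading the curve may understate. Censoring at surgery is defensible in a study of disease progression, and insufficiency can still develop after a regional pancreatectomy, so that event does not preclude the endpoint as death does. This stands as a reason to make the plan state its target. It does not rescue the label, because 1-KM matches the natural-course reading only under an unstated independence assumption.

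The size is wholly assumed. At a competing hazard of 0.01 per year the gap is about one point or less. The top figures need 0.04 per year, a net risk of 1 − exp(−0.04 × 8) = 27% by year 10. The larger group effects need a fourfold difference in competing hazards, which nothing in the documents establishes; with equal hazards the difference moves by about 0.5 points at most. All of this stands. One title in the protocol's reference list does link CFTR variants to a higher pancreatic cancer risk, and CFTR is among the genes that define the genetic-positive group. That justifies counting events by group but shows nothing about this cohort.

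The plan never uses the word censored. That too is correct, but no other handling is described. Finally, no p-value or hazard ratio changes, which I accept.

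**Conclusion.** The concern holds in its conditional form. If cancer, pancreatectomy or death occurs among patients still at risk, the planned curves overstate the probability of insufficiency before those events, and nothing in the plan corrects this. If there are no such events, the two estimates coincide.

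Under constant, independent hazards with insufficiency at 0.05 per year, the plausible 10-year overstatement runs from 0.1 to 4.0 points, and it may well be under one point. Absolute group gaps can be misstated in either direction if competing events differ by group; the documents do not show whether they do.

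The defect is confined to the curves, the absolute rates read from them and the wording of the group comparison. Log-rank and Cox results stand when read as cause-specific. It should be fixed because the label on the primary-endpoint curves is wrong as written and the correction is cheap. Confidence is medium, since the size cannot be learned from the documents.

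**What to change.** In both the SAP and protocol section 7:

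- Estimate the cumulative incidence of the primary endpoint, and of diabetes and steatorrhea separately, by Aalen-Johansen, with death, pancreatic cancer and pancreatectomy as competing events. State that the quantity is insufficiency before those events.
- Keep end of follow-up and last personal contact as ordinary censoring.
- Report the number of each competing event by genetic and environmental group.
- Keep log-rank with Bonferroni and Cox, labelled cause-specific, and say that the log-rank test compares cause-specific hazards.
- If insufficiency after pancreatectomy was recorded, add a sensitivity analysis that counts it.
- If a natural course without surgery is what is meant, say so, label the curve as one minus Kaplan-Meier with these events censored, and state the independence assumption.

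The cost is SAP wording and a different estimator for the curves. The date and reason that follow-up ended must be available. The section 5 definition implies this, but the recorded items ("The examination results, any changes in alcohol consumption or smoking status, and CP complications are also recorded") do not list the reason. Reported rates will be slightly lower, and the curves will no longer map directly onto the hazard ratios, so they should be shown alongside the event counts and Cox results. Aalen-Johansen does not correct for deaths before enrolment, which this cohort cannot contain, and the report should say so.

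### Bonferroni for the pairwise log-rank tests is valid, but Holm's step-down rule keeps the same 5% family-wise bound and can only reject more: an optional, cheap improvement

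*Combined protocol and SAP*

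**What the plan says.** The wording is identical in the protocol (section 7, Statistical analysis) and in the Statistical Analysis Plan. Curves are compared by log-rank test: "Log-rank test is further used to analyze the difference of cumulative rates of pancreatic insufficiency between two groups". The multiplicity rule follows: P "values for pairwise comparisons were adjusted using the Bonferroni correction". Testing is two-sided. A Cox model follows ("Cox proportional hazards regression model is used to identify the potential risk factors"), reported as "Hazard ratios and 95% confidence intervals are calculated"; no adjustment is stated for it.

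The groupings are in protocol section 5. Genetic status (G) and environmental status (E) each have two levels. For alcohol, "the patients are categorized into four groups, abstainers, light drinkers", then moderate and heavy drinkers. The documents do not state alpha, a sample size, an expected number of events, which groups are compared pairwise, or whether G and E are crossed into four cells.

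**The concern.** Single-step Bonferroni holds every pair to the same strict threshold, however many other pairs are already clearly different. Holm starts at that threshold and relaxes it after each rejection. It needs no further assumption about dependence between the tests and keeps the same bound on the family-wise error. It rejects everything Bonferroni rejects, and sometimes more.

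The study's objective covers both genetic and environmental factors. If four groups are compared, the pair that differs most may be easy to reject yet say little about which factor is responsible. The pairs that differ in one factor only are more informative, and those are the ones that can gain from the relaxed thresholds. At stake is some avoidable loss of power in the only comparisons for which the plan states multiplicity control.

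**Working it through.** The plan gives no power or threshold figure to reproduce, so this check compares the two rules under stated assumptions.

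**Inputs.** From the documents: Bonferroni, two-group log-rank tests, two-sided testing, a four-level alcohol grouping, and two-level G and E. Assumed: alpha 0.05 (suggested by the 95% intervals), all pairs of four groups tested, equal events d per group, multiplicative effects, and normally distributed log hazards with variance 1/d.

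**Thresholds.** Number of pairs: m = 4 × 3 / 2 = 6.
- Bonferroni: 0.05/6 = 0.00833 for every pair.
- Holm: 0.05/(6 − i + 1) for the i-th smallest P value, that is 0.00833, 0.0100, 0.0125, 0.0167, 0.025 and 0.05.
- With m = 1, both are 0.05.

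**Bonferroni controls the error.** For six independent tests the family-wise error is 1 − 0.95⁶ = 0.265 unadjusted and 1 − (1 − 0.00833)⁶ = 0.049 with Bonferroni. Simulated for the six correlated pairs with no true differences, it is about 4.2% under either rule.

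**Power for a single-factor pair.** For Bonferroni, power ≈ Φ(|log HR| / √(2/d) − 2.638), where 2.638 is the two-sided critical value at 0.00833. For d = 100:
- HR 0.7: 0.3567/0.1414 = 2.522, and Φ(−0.116) = 45%.
- HR 1.4: 0.3365/0.1414 = 2.379, and Φ(−0.259) = 40%.

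Holm was simulated (at least 200,000 replicates) with HR 0.7 for G and 1.4 for E. Each range runs from the E pair to the G pair:

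| Events per group | Bonferroni | Holm | Gain, points |
|---|---|---|---|
| 50 | 17–20% | 20–23% | about 3 |
| 100 | 40–45% | 48–53% | about 8 |
| 150 | 61–67% | 71–76% | 9–10 |
| 200 | 77–82% | 86–89% | 7–9 |

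The chance of rejecting all four single-factor pairs rises from 20% to 40% at 150 events per group, and from 44% to 65% at 200.

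**Other assumed effects.** These hazard ratios put 1.4/0.7 = 2.0 on the extreme pair, which makes the first rejection easy and so favours Holm. With other patterns and 100 to 600 events in total, the average gain per truly different pair is 1 to 7 points:
- E effect only, HR 1.6: 38.6% to 42.2% at 200 events, and 75.3% to 80.1% at 400.
- G HR 1.4 and E HR 1.6, 600 events: 68.9% to 75.8%. The largest gain for any one pair, 60.8% to 74.2%, also occurs here.

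**What does not change.** Holm's first step uses Bonferroni's threshold, so the chance of at least one rejection is identical (for example 72.8% under both at 200 events with the E effect only).

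**What it costs in error.** With two of the six pairs truly null and the others different, the actual family-wise error is about 1.7% for Bonferroni. For Holm it is 4.1% at 600 events with HR 1.6, and 4.9% when the E effect is large.

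**The case against.** The strongest reply is that Bonferroni is prespecified, valid under any dependence and stated consistently in both documents, so that preferring Holm is a matter of taste. The first part stands: nothing here is an error. But validity does not show that Bonferroni has an advantage this plan relies on. Its matching simultaneous intervals are such an advantage in principle, and the plan states only ordinary 95% intervals.

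A second reply also stands. Part of Holm's extra power is paid for by a higher actual family-wise error when some pairs differ. A reader might infer that Bonferroni gives up power in return for nothing; the figures of 1.7% against up to 4.9% contradict that, although both respect the 5% bound.

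Third, a reader might infer that the plan will miss real genetic or environmental effects. The documents do not support this. They list no six-pair family, state no G-by-E crossing, and give no event counts or effect sizes from which a loss could be shown. Moreover, the analysis named for identifying risk factors is the Cox model, for which no Bonferroni adjustment is stated. Power also depends far more on the unstated number of events than on the choice of rule: at HR 1.6 and threshold 0.00833 it is 39%, 75% and 92% with 100, 200 and 300 events in the pair.

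**Conclusion.** The point holds as an optional improvement. Where a grouping yields several pairwise tests, Holm keeps the same 5% bound and may detect differences that Bonferroni misses. The gain is about 3 to 10 points for a single-factor pair, given alpha 0.05, four equal groups, all six pairs tested, hazard ratios of 0.7 and 1.4, and 50 to 200 events per group. None of these conditions is stated in the documents, apart from the existence of a four-level alcohol grouping, and other assumed effects give average gains of 1 to 7 points. There is no gain in the chance of finding any difference, none with a single comparison, and no effect on the Cox hazard ratios. Reading this as a flaw that invalidates the planned analysis would go beyond the documents.

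**What to change.** Before outcomes are analysed, name the Holm step-down procedure in place of Bonferroni in protocol section 7 (Statistical analysis) and in the SAP. State in the same sentence that the family is all pairwise comparisons of one grouping for one endpoint, and give alpha. Bonferroni needs that definition just as much, so it is worth adding even if the rule is kept.

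The cost is a sentence in each place and no new data. Two consequences should be accepted knowingly: an actual family-wise error above Bonferroni's when some pairs differ, though at most 5%, and no simple simultaneous intervals to match the adjusted P values. The second matters only if such intervals are later wanted.
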